We will follow the FDA's Guidance for evaluating and monitoring potential drug-induced hepatotoxicity. Subjects with stable liver disease can be included if they have a normal total bilirubin and prothrombin time/INR at baseline. Liver function tests (ALT, AST, ALP and bilirubin) will be drawn at baseline and at each visit while subjects are on study drug. In addition, if these labs are abnormal at the end of study visit they will be repeated at the safety follow up visit two weeks later and repeated until back to baseline values. During each phone call that assesses effects of study drug, nonspecific symptoms of Drug Induced Liver Injury (DILI) will be checked, e.g., anorexia, nausea, fatigue, right upper abdominal discomfort, and vomiting. If symptoms indicative of DILI occur the subject will return to clinic immediately for measurement of laboratory signs of hepatic injury, regardless of when the next visit or monitoring interval is scheduled. At any time if aminotransferase enzymes are greater than 3x upper limit of normal (ULN), we will repeat ALT, AST, ALP and bilirubin within 48-72 hours. If symptoms persist or repeat testing shows aminotransferase >3xULN for subjects with normal baseline measures or 2-fold increases above baseline values for subjects with elevated values before drug exposure, we will initiate close observation to determine whether the abnormalities are improving or worsening. Per the FDA, close observation includes:

- Repeating liver enzyme and serum bilirubin tests two or three times weekly. Frequency of retesting can decrease to once a week or less if abnormalities stabilize or the trial drug has been discontinued and the subject is asymptomatic.
- Obtaining a more detailed history of symptoms and prior or concurrent diseases.
- Obtaining a history of concomitant drug use (including nonprescription medications and herbal and dietary supplement preparations), alcohol use, recreational drug use, and special diets.
- Ruling out acute viral hepatitis types A, B, C, D, and E; autoimmune or alcoholic hepatitis; NASH; hypoxic/ischemic hepatopathy; and biliary tract disease.

- Obtaining a history of exposure to environmental chemical agents.
- Obtaining additional tests to evaluate liver function, as appropriate (e.g., INR, direct bilirubin).
- Considering gastroenterology or hepatology consultations.

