We will gather further history as recommended. Unless we find that the repeat testing shows the aminotransferase levels decline to baseline, we will consult the UCH Hepatology team to determine further management.

The FDA advises that since transient fluctuations of ALT or AST are common, and progression to severe liver injury or failure is uncommon, automatic discontinuation of trial drug upon finding a greater than 3xULN elevation of ALT or AST may be unnecessary. The decision of whether to stop study drug will be affected by information on related drugs, the accumulating clinical experience, the clinical status of the patient, and many other factors. We will consult the UCH hepatology service and keep the following FDA guidance in mind. The FDA states that discontinuation of treatment should be considered if:

ALT or AST >8xULN

ALT or AST >5xULN for more than 2 weeks

ALT or AST >3xULN **and** (TBL >2xULN **or** INR >1.5)

ALT or AST >3xULN with the appearance of fatigue, nausea, vomiting, right upper quadrant pain or tenderness, fever, rash, and/or eosinophilia (>5%)

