## **Stage 2: Randomized Controlled Trial**

For the RCT the analysis will be performed in accordance with the analysis plan devised prior to unblinding. Baseline variables will be examined for equality between the two sequence groups. The primary, secondary and exploratory outcomes will be analyzed as below for both the low dose (5 mg/kg/day) and highest tolerated dose.

Primary Specific Aim: To evaluate the safety and tolerability of CBD, in the form of Epidiolex, in PD.

The primary outcome is safety and tolerability and will be assessed in 4 ways:

1. Frequency of study-related adverse events at each dose level collected at standardized phone script administration and at study visits. Analysis (frequency of study-related adverse events at each dose level in the two groups, treatment vs. placebo) will be mostly descriptive, and proportions and confidence intervals will be calculated. Contrasts involving repeated measures on the same subjects can be tested with McNemar's test (for two correlated proportions) or GEE models/GLMMs. Contrasts for independent data can be tested with standard two sample proportions test and with GLMs. Proportions, logistic regression, and relative risk regression can be applied to binary outcomes over a fixed period of time, and Poisson models can be applied to counts or events over time.
2. Vital signs, orthostatic blood pressures, physical exam, EKG and labs (hematology, complete metabolic profile, urinalysis) during study visits. For vital signs and labs, data will be analyzed as a simple two-period crossover trial. Means and confidence intervals will be presented for each group \* treatment, and for the change scores in each group. A two sample T-test will compare the means of the two groups, those in the CBD-placebo group vs. those in the placebo-CBD group, on the change scores between period 1 to period 2. The difference between the means of the two group will be equal to twice the treatment effect. Physical exam and EKG will be descriptive between the two groups (treatment vs. placebo). More complex situations, including testing for treatment \* order interaction, can be analyzed with longitudinal regression models.

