3. Standardized assessment tools (MoCA, Cognition assessment battery, Anxiety short form, NPI, SCOPA-Sleep, RBDSQ, QUIP-RS, C-SSRS, Depression short form, Emotional Behavioral dyscontrol short form, Fatigue severity scale, MDS UPDRS, UDysRS, Pain Intensity 3a short form and Pain Intensity 4a short form, IRLS, PDQ-39 and EQ-5D-5L) and lab tests, the data will be analyzed as a simple two-period crossover trial. Means and confidence intervals will be presented for each group \* treatment, and for the change scores in each group. A two sample T-test will compare the means of the two groups, those in the CBD-placebo group vs. those in the placebo-CBD group, on the change scores between period 1 to period 2. The difference between the means of the two group will be equal to twice the treatment effect. More complex situations, including testing for treatment \* order interaction, can be analyzed with longitudinal regression models.
4. Proportion of subjects drop out of the study due to study drug intolerance. Analysis (proportions of subjects drop out of the study due to study drug intolerance in the two groups, treatment vs. placebo) will be mostly descriptive, and proportions and confidence intervals will be calculated. Proportion differences between groups can be compared with the standard test.

The difference between the mean change scores of the two group will be equal to twice the treatment effect. We will test the null hypothesis of no treatment effect. To test and control for a possible time/order effect, longitudinal regression models will be fit with a time/order variable included.

Secondary Specific Aim is to examine the effect of CBD on severity & duration of intractable tremor in PD.

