### **Stage 2: Randomized Controlled Trial**

The primary outcome, safety and tolerability, will mostly be analyzed descriptively. For the main secondary outcome, testing for a treatment effect on tremor, a sample size of 38 patients would achieve 90% power with an alpha level of 0.05, a standard deviation of the differences of 3 units on the outcome scale, and an absolute value mean effect on the outcome scale of 1.625, approximately 25% (this would be a clinically significant effect). We anticipate a dropout rate of 10%, necessitating 43 patients, and we then increase to 48 for safety, rounding and because of the 2x2 stratification plan. Note that each patient serves as his/her own matched control.

Since other outcomes are either descriptive and/or exploratory, and sample size is limited, there will be no adjustment for multiple testing adjustments are not planned.

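### Stage 2 labs are compared only through means, so individual liver-enzyme rises above the protocol's own ULN limits are not tabulated by treatment

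*Combined protocol and SAP*

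**What the plan says.** Section F, Stage 2, assesses the primary outcome in four ways. Item 2 covers labs: "For vital signs and labs, data will be analyzed as a simple two-period crossover trial". The summary is "Means and confidence intervals will be presented for each group" by treatment, and the test is "A two sample T-test will compare the means of the two groups" on the change from period 1 to period 2. Longitudinal regression is optional. Item 3 repeats this method for lab tests. Stage 1 uses means and a paired t-test. Section F plans no shift table, no count above a ULN multiple, no highest on-treatment value and no combined aminotransferase and bilirubin summary.

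Section D treats the liver differently. It acts on the single subject: "At any time if aminotransferase enzymes are greater than 3x upper limit of normal (ULN") leads to repeat testing. For subjects whose values were raised before dosing, it uses a doubling over baseline. The listed grounds for considering discontinuation include "ALT or AST >8xULN", more than 5x ULN lasting over two weeks, and more than 3x ULN together with raised bilirubin, raised INR or symptoms.

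Two other parts of the primary outcome are counts. Item 1 is "Frequency of study-related adverse events at each dose level collected at standardized phone script administration and at study visits", and item 4 is "Proportion of subjects drop out of the study due to study drug intolerance".

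**The concern.** Liver injury from a drug may appear as a large rise in a few subjects rather than a small shift in everyone. A comparison of means is poorly suited to that pattern: a few extreme values move the mean only a little and inflate the standard deviation used to judge it. Section D recognises this by setting individual limits, but section F drops them.

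Safety and tolerability is the primary aim, and section C.9 names raised liver tests among the reported effects of CBD. At stake is whether a reader of the primary results can see how many subjects crossed 3x, 5x or 8x ULN on CBD and how many on placebo.

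Two details widen the gap. Section F specifies analyses at the low dose and the highest tolerated dose. A metabolic profile is also drawn at the 20 mg/kg/day visit (C.3, Visits 4 and 8), and section D adds repeat draws within 48 to 72 hours. For a subject who goes beyond 20 mg/kg/day, as the Stage 2 schedule shows, a peak at that visit enters no stated lab comparison, and nor does one on a repeat draw. Also, a related grade 3 or 4 event stops study drug permanently (C.2), so a subject stopped in period 1 may have no on-drug period 2 value for a change score.

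**Working it through.** **Plan's own figures.** The documents give no figure for the lab comparison. The only Stage 2 calculation is for tremor: 38 patients, SD of differences 3, effect 1.625, alpha 0.05 (taken as two-sided). A noncentral t calculation gives 90.2% power (paired) or 90.1% (two-sample crossover form), so it reproduces. 38/0.9 = 42.2, hence 43, then 48 by the plan's rounding. It bears on labs only by supplying N = 48, or 24 per sequence.

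**Step 1: the planned test with no other variation.** Let k subjects rise by h on CBD only, k1 in one sequence and k2 in the other, with n = N/2.

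- Difference between the sequence means of the change scores: kh/n. Half of this, kh/N, is the estimated treatment effect.
- Pooled variance: h²[k − (k1² + k2²)/n]/(N − 2).
- t = (k/n) / √{[k − (k1² + k2²)/n]/(N − 2) × 2/n}.

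The h cancels, so without other variation t does not depend on the size of the rise. Example: N = 48, k1 = 2, k2 = 1 gives 0.125/√{[(3 − 5/24)/46] × (2/24)} = 0.125/0.0711 = 1.76.

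| k | t at N = 48 (all splits between sequences) | critical value |
|---|---|---|
| 1 | 1.00 | 2.013 |
| 2 | 1.41 to 1.45 | 2.013 |
| 3 | 1.76 to 1.81 (p 0.076 to 0.085) | 2.013 |
| 4 | 2.04 to 2.14 | 2.013 |

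**Step 2: simulation with ordinary variation.** Assumptions, none from the documents: ALT median 20 U/L, between-subject log-SD 0.35, visit noise 15%, 48 subjects, k rises to about 200 U/L on CBD only. Several independent runs gave p<0.05 in 0% of trials for k = 1, 0% for k = 2, about 1% to 2% for k = 3 and 57% to 67% for k = 4. The spread reflects simulation error and how the peak is modelled. Three such rises shift the mean by about 3 × (200 − 20)/48 = 11 U/L.

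**Step 3: other assumptions.** Usual ALT 0.6 ULN, within-subject SD 0.15 to 0.25 ULN, rises to 3, 5 or 8x ULN, N = 43 and 48. Chance of p<0.05: k = 1, 0% to 4%; k = 2, 0% to 8%; k = 3, 2% to 19%; k = 4, 35% to 66%. Three rises to 5x ULN in 48 subjects move the mean by 3 × (5 − 0.6)/48 = 0.28 ULN.

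**Step 4: the same data as counts.** 3/48 = 6.3%, Clopper-Pearson 95% CI 1.3% to 17.2%; 3/43 = 7.0%, 1.5% to 19.1%. Exact McNemar p for k:0 is 2 × 0.5^k: 0.25 for 3:0, 0.125 for 4:0, 0.0625 for 5:0, 0.031 for 6:0.

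**The case against.** The strongest reply is that labs are one part of four. A reader might infer that large enzyme rises would be invisible in the primary safety analysis; the documents do not support that. Items 1 and 4 count related adverse events and intolerance dropouts by treatment, and the protocol provides routes into those counts. Serious abnormal lab values must be documented within 24 hours (C.8). An event is related unless a listed exclusion applies (C.8). The grade 1 definition covers diagnostic findings without symptoms (C.2). Two subjects with the same related event of grade 3 or above meet a study stopping criterion (C.7). Table 3 in C.9 already lists a raised AST as an adverse reaction. This stands in part: the routes depend on investigator recording and causality judgment, and a more likely cause such as a concomitant drug makes an event unrelated.

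A reader might also infer that the larger the rise, the weaker the t-test. That holds here for up to three subjects and reverses at four: with the Step 2 assumptions, rejection at k = 4 goes from 36% for rises to 60 U/L to above 70% for rises to 320 U/L.

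Third, a paired test of counts is no more powerful. It cannot reach p<0.05 before 6:0, whereas the planned t-test rejects in roughly 60% of trials at four rises to 200 U/L and nearly always at five. This stands, and it rules out McNemar's test as the main comparison.

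Last, the plan says "The primary outcome, safety and tolerability, will mostly be analyzed descriptively", and nothing in it says that a non-significant mean would be reported as no hepatic effect. That is fair, but a descriptive analysis is where counts of threshold crossings belong.

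**Conclusion.** The point holds in a limited form. Section F compares Stage 2 labs only through means, and section D's individual liver limits are not carried into any analysis. Up to three large CBD-only rises among 48 subjects would usually not be flagged by the lab comparison: about 1% to 2% rejection for three rises to 200 U/L, or 2% to 19% across the alternative assumptions. Four rises give roughly 60% (35% to 66% under the alternatives). These rates rest on assumed ALT distributions. The no-variation result, t of about 1.8 against a critical 2.01 for three rises, rests only on N and k.

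Such rises could still reach the primary outcome as related adverse events or dropouts, but no stated rule guarantees it. This is a reporting gap worth closing before unblinding; it does not invalidate the safety analysis.

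**What to change.** In section F, Stage 2, item 2, add a descriptive table by treatment received (CBD, placebo). For each subject take the highest on-treatment value of each liver test, including the 20 mg/kg/day visit and unscheduled repeat draws. Report number, percentage and exact 95% confidence interval for:

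- ALT or AST above 3x, 5x and 8x ULN, with the two-week duration criterion for 5x where repeat draws allow it;
- ALT or AST above 3x ULN combined with the bilirubin or INR limits in section D;
- for subjects with raised values before dosing, the doubling over baseline in section D.

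Use as denominator the subjects with at least one lab value on that treatment, so that a subject who stops in period 1 still counts. Keep the mean comparison alongside. Do not make McNemar's test the main comparison.

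The limits are taken from the protocol as they stand and used only for tabulation; no clinical rule changes. The cost is a few lines of analysis text and one table from data already collected. With few events the intervals will be wide, and the table adds visibility, not power.

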## **Sample Size Justification**

### **Stage 1. Open Label Dose Escalation Tolerability Study**

Ten patients are recruited to the safety study. A 95% confidence interval derived from the T distribution, for a continuous outcome, would have a total width of 1.43 times the standard deviation of the change score. For the test for a difference, with an alpha level of 0.05, an effect size of 1.00 relative to the standard deviation would be required for 80% power, and an effect size of 1.16 would be required for 90% power. For a binary event, the probability of no "success" in 10 independent runs is less than 5% if the true probability is 26% or greater, and less than 2.5% if the true probability is 31% or greater.

### **Stage 2: Randomized Controlled Trial**

The primary outcome, safety and tolerability, will mostly be analyzed descriptively. For the main secondary outcome, testing for a treatment effect on tremor, a sample size of 38 patients would achieve 90% power with an alpha level of 0.05, a standard deviation of the differences of 3 units on the outcome scale, and an absolute value mean effect on the outcome scale of 1.625, approximately 25% (this would be a clinically significant effect). We anticipate a dropout rate of 10%, necessitating 43 patients, and we then increase to 48 for safety, rounding and because of the 2x2 stratification plan. Note that each patient serves as his/her own matched control.

Since other outcomes are either descriptive and/or exploratory, and sample size is limited, there will be no adjustment for multiple testing adjustments are not planned.

## **G. Summarize Knowledge to be Gained:**

Marijuana is one of the most used alternative medications. Since it became legal and readily available in Colorado, Parkinson disease (PD) and other movement disorders patients have been trying it, usually without the knowledge of or supervision of their neurologist. This study will promote the safety of our patients and provide data useful in evaluating the effect and safety of CBD on tremor, cognition, anxiety, psychosis, and other symptoms, including sleep, impulsivity, suicidality, mood, fatigue, restless legs syndrome, pain, bradykinesia, rigidity, balance, and dyskinesia in PD patients. Data from this study are essential to aid in designing future marijuana research.

Appendix A Schedule of events Stage 1 Open label dose escalation tolerability study												
	Screening	Baseline	Treatment Period							Safety Followup		
Week		1	1-4							4	5-6	6
day	< negative 21	1	1-3	4-6	7-11	12-16	17-19	20-25	26-31 (k)	27-29	30-39	40 (+/- 4)
Clinic visit	1	2							3			4
Telephone call*			1	2	3	4	5	6 (h)		7(i)	8(h)	
Dosage of CBD or placebo mg/kg	0	5(take the first dose in clinic)	5	7.5	10	15	20	20	20 (take the study drug prior to clinic visit)	0	0	0
Informed consent	√											
Eligibility Criteria	√	√										
Demographics	√											
Medical History (a)	√											
Family medical history	√											
Medical History - interval	√	√	√	√	√	√	√		√	√		√
Concomitant Medications	√	√	√	√	√	√	√		√	√		√
Study drug compliance check									√			
Dispense study drug and instruction		√										
Adverse Events (b)			√	√	√	√	√		√	√		√
Formal drug interaction assessment	√	√							√			√
Vital Signs(c)	√	√ (l)							√ (n)			√
Orthostatic Blood Pressures check	√	√ (l)							√ (n)			√
Height and Weight	√	√							√			√
Complete Physical Exam (d)	√								√			√
Neurological exam	√								√			
Brief physical exam (heart and lung auscultation)		√										
Hematology (e)	√								√			√ (j)
Hemoglobin A1C	√											
Complete metabolic profile (f)	√								√			√ (j)
Blood cannabis analysis	√								√ (m)			√
Urinalysis (g)	√								√			√ (j)
Urine Drug (THC) test		√										
Urine CBD and metabolites levels test (o)									√			
Urine cups dispense and urine collection instruction		√										
ECG (12-LEAD)	√								√			√ (j)
Serum Pregnancy Test (for women childbearing potential)	√											
Urine Pregnancy Test (for women childbearing potential)		√							√			√
Assessment of past marijuana use	√											
Drug, alcohol and tobacco abuse screening test	√											
MOCA	√								√			√
MDS-UPDRS part III	√											
MDS-UPDRS		√							√			√
Unified Dyskinesia Rating Scale (UDysRS)		√							√			√
H & Y rating	√								√			√
QUIP-RS	√								√			√
C-SSRS	√	√							√			√
NPI	√								√			√
SCOPA-sleep	√		√	√	√	√	√		√	√		√
RBDSQ		√							√			√
IRLS		√							√			√
Anxiety short form	√								√			√
Depression short form	√								√			√
Emotional behavioral dyscontrol short form	√								√			√
Fatigue severity scale	√								√			√
Pain intensity and interference short form	√								√			√
CGI									√			
PGI									√			
Home diary dispense & instruction		√										
Home diary collection & review									√			
Fax, mail or email a copy or image of the diary filled out				√								

\* phone call is made on the third day of each dose (between 5-10 mg/kg/day) and fifth day of each dose (between 10-20 mg/kg/day)

## Schedule of Event- Stage 1 note

Note: regarding the rows of days and weeks, it is variable, because of note k and also because some patients will take shorter or longer to get to their maximum tolerated dose than those that titrated to 20 mg/kg/day.
a. A complete medical history (including PD history, mental health history, alcohol and drug use) will be obtained from the subject at the Screening Visit and recorded on the appropriate CRF. The medical history and other enrollment criteria will be reviewed and updated at the Baseline/Day 1 visit to determine continued eligibility for the study.
b. Adverse events will be recorded from the time of the first dose of study drug. Any subject with an ongoing AE will be followed until the AE is resolved, returns to baseline or deemed stable by the investigator.
c. Vital signs obtained after the subject has been sitting for at least 5 minutes. Body temperature will be obtained at screening, Day 1, and at the final follow up visit. Blood pressure, respiratory rate and heart rate will be measured once each day assessed. During screening only, after the seated blood pressure has been obtained, the blood pressure will be repeated within 3 minutes of the subject standing up. This procedure may be repeated, if appropriate, following hydration. If repeated, a total of two additional pairs of BP assessments (sitting/standing) should be obtained, and the results of the last attempt should be reported.
d. Complete PE to include: skin, head-neck, eyes-ears-nose-throat, lungs-chest, heart, abdomen, extremities, neurological.
e. Hematology consists of hemoglobin, hematocrit, mean corpuscular volume (MCV), mean corpuscular hemoglobin concentration (MCHC), red blood cell count (RBC), white blood cell (WBC) count, WBC differential (absolute), and numerical platelet count.
f. Serum chemistry (fasting not required) consists of alkaline phosphatase, albumin, blood urea nitrogen, calcium, carbon dioxide, chloride, creatinine (MDRD formula for eGFR, to be done by the central laboratory), $\gamma$ -glutamyltransferase, glucose, inorganic phosphorus, potassium, alanine aminotransferase, lactate dehydrogenase, aspartate aminotransferase, sodium, total bilirubin, and total protein.
g. Urinalysis will be performed locally using sponsor-supplied dipsticks, including leukocytes, specific gravity, pH, protein, ketones, glucose, nitrite, blood, urobilinogen, and bilirubin. If nitrite, blood, or protein tests are positive, a microscopic examination will be performed at the central laboratory.
h. Call patient to remind them the clinical visit next day
i. Call patient to collect adverse events and information of signs of withdrawal
j. Hematology, chemistry, urinalysis and EKG will be done if there was a clinically significant change at the end of study visit compared to baseline visit.
k. For some patients, the visit can occur during 10-15 days on max dose, not just on the 10th day.
l. Subject will be monitored and vital signs will be checked at before and 1 hour after taking the study drug.
m. Blood draw will be performed 3 hours after taking the study drug of the clinical visit day.
n. Subject will be monitored and vital signs will be checked at before and 1 and 3 hours after taking the study drug.
o. Clean catch urine collection after taking the study drug. Urine is collected in a 500 mL container and stored in 3-4 samll cups (120 mL, fill up to 3/4).

# Schedule of Event—Stage 2

Appendix B schedule of event Stage 2 RCT		schedule of events																															
week (number of days)	screening	baseline		Treatment Period														Washout			Treatment Period										Safety Followup		
		1	1-3	4-9	1-7 (47 days)														7 to 10 (21 days)			10 to 17 (47 days)										17	17 to 19 (10 days)
Days	<negative 21	1	1-3	4-9	10 (+5) (k)	11-13	14-16	17-21	22-24	25-34	35-44	45-48	49 (+/- 4) (l)	50-52	53-69	70	71	71-73	75-79	80 (+5) (k)	81-83	84-86	87-91	92-94	95-104	105-114	115-118	119 (+/- 4) (l)	120-122	123-132	133 (+/- 4)		
Dosage of CBD or placebo mg/kg	0	5 (take the first dose in clinic)	5	5	5 (take the study drug prior to clinic visit)	10	15	20	25	25	25	25	25 (take the study drug prior to clinic visit)	0	0	0	5	5	5	5 (take the study drug prior to clinic visit)	10	15	20	25	25	25	25	25 (take the study drug prior to clinic visit)	0	0	0		
Clinical visit*	1	2		3			4						5			6			7			8					9				10		
Telephone call**			1	2 (l)		3	4 (q)		5	6	7	8 (i)		9 (j)		10 (i)		11	12 (i)		13	14 (q)		15	16	17	18 (i)		19 (i)	20 (j)			
Informed consent	✓																																
Eligibility Criteria	✓	✓																															
Demographics	✓																																
Medical History (a)	✓																																
Medical History	✓	✓	✓	✓	✓	✓	✓	✓	✓	✓	✓	✓	✓	✓	✓	✓	✓	✓	✓	✓	✓	✓	✓	✓	✓	✓	✓	✓	✓	✓	✓		
Family medical history	✓																																
Concomitant Medications	✓	✓	✓	✓	✓	✓	✓	✓	✓	✓	✓	✓	✓	✓	✓	✓	✓	✓	✓	✓	✓	✓	✓	✓	✓	✓	✓	✓	✓	✓	✓		
Randomization		✓																															
Blinding assessment					✓								✓								✓												
Study drug compliance check					✓								✓								✓												
Dispense study drug and instruction		✓			✓			✓									✓				✓												
Adverse Events (b)			✓	✓	✓	✓	✓	✓	✓	✓	✓	✓	✓	✓	✓	✓	✓	✓	✓	✓	✓	✓	✓	✓	✓	✓	✓	✓	✓	✓	✓		
Formal drug interaction assessment	✓	✓			✓			✓					✓				✓			✓			✓				✓				✓		
Vital Signs (c)	✓	✓ (n)			✓ (g)			✓					✓ (p)				✓ (n)			✓ (p)			✓					✓ (g)			✓		
Orthostatic Blood Pressures check	✓	✓ (n)			✓ (p)			✓					✓ (p)				✓ (n)			✓ (p)			✓					✓ (g)			✓		
Height and Weight	✓	✓			✓			✓					✓				✓			✓			✓					✓			✓		
Complete Physical Exam (d)	✓												✓															✓			✓		
Neurological exam (e)	✓												✓															✓			✓		
Brief physical exam (heart and lung auscultation)		✓			✓			✓													✓		✓										
Hematology (f)	✓												✓															✓			✓ (m)		
Hemoglobin A1C	✓																																
Complete metabolic profile (g)	✓				✓			✓					✓								✓							✓			✓ (m)		
Blood cannabis analysis	✓				✓ (o)								✓ (o)								✓ (o)							✓ (o)			✓		
Urine analysis (h)	✓												✓															✓			✓ (m)		
Urine drug (THC) test		✓																															
Urinary CBD and metabolites levels test *					✓			✓					✓								✓						✓						
Urine cups dispense and urine collection instruction		✓			✓			✓									✓				✓												
EKG (12-LEAD)	✓												✓															✓			✓ (m)		
Serum Pregnancy Test (for women childbearing potential)	✓																																
Urine Pregnancy Test (for women childbearing potential)		✓			✓								✓								✓							✓			✓		
Assessment of past marijuana use	✓																																
Drug, alcohol and tobacco abuse screening test	✓																																
MOCA	✓	✓			✓								✓								✓							✓			✓		
Cognitive assessment battery	✓	✓											✓								✓							✓			✓		
MDS-UPDRS part III	✓												✓								✓							✓			✓		
MDS-UPDRS (all 4 parts)	✓	✓			✓								✓								✓							✓			✓		
H & Y rating	✓	✓			✓								✓								✓							✓			✓		
BPM	✓	✓			✓								✓								✓							✓			✓		
QUIP-RS	✓	✓			✓								✓								✓							✓			✓		
E-SSRS	✓	✓			✓								✓								✓							✓			✓		
RBDSQ	✓	✓			✓								✓								✓							✓			✓		
NPI	✓				✓								✓								✓							✓			✓		
Anxiety short form	✓		✓	✓	✓				✓	✓			✓							✓	✓	✓					✓	✓	✓	✓	✓		
Depression short form	✓		✓	✓	✓				✓	✓			✓							✓	✓	✓					✓	✓	✓	✓	✓		
Emotional and behavioral dyscontrol short form	✓		✓	✓	✓				✓	✓			✓							✓	✓	✓					✓	✓	✓	✓	✓		
SCOPA-deep	✓		✓	✓	✓	✓	✓	✓	✓	✓	✓	✓	✓							✓	✓	✓	✓	✓	✓	✓	✓	✓	✓	✓	✓		
RLS	✓	✓			✓								✓								✓							✓			✓		
Fatigue severity scale	✓				✓								✓								✓							✓			✓		
Pain intensity and interference short form	✓				✓								✓								✓							✓			✓		
PDO-39	✓	✓			✓								✓								✓							✓			✓		
EQ-5D	✓	✓	✓	✓	✓				✓	✓			✓								✓	✓	✓				✓	✓	✓	✓	✓		
CGI					✓			✓					✓								✓							✓			✓		
PGI					✓			✓					✓								✓							✓			✓		
Unified Dyskinesia Rating Scale (UDyRS)	✓				✓								✓								✓							✓			✓		
Home diary dispense & instruction	✓				✓			✓					✓								✓							✓			✓		
Home diary collection & review					✓			✓					✓								✓							✓			✓		

\*Clinical visit: visit 3 and 5 are low dose visits, 10th day of 5 mg/kg/day, visit 4 and 6: end of first and second treatment phase.  
 \*\*phone call is made on the third day of each dose; x means the phone call is only to remind subject to come in for visit the next day.

Note: regarding the rows of days and weeks, it is variable, because of note (k) and note (l), and because some patients will take shorter or longer to get to their maximum tolerated dose than those that titrate to the target dose (determined in stage 1).

